10.7.2.2. Handling of PK Concentration Data

Element	Reporting Detail
General	If a PK sample in a profile is 'no result', 'no sample received', or 'insufficient sample', data will be set as missing. No imputation will be applied.

10.8. Appendix 8: Values of Potential Clinical Importance

10.8.1. Laboratory Values

Division of AIDS (DAIDS, Version 2.0, November 2014) AE grade 2 and above of lab abnormalities will be listed by subject, period/treatment, visit, and actual date and time.

Statistics and Programming group will use this version to add toxicity grades values in the ADAM dataset.

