5.4.4. Neutropenia Stopping Criteria

Subjects with an absolute neutrophil count (ANC) less than $1 \times 10^9/L$ will be discontinued from study treatment. The presence of ANC less than $1 \times 10^9/L$ and a single measured temperature of $>38.3 \text{ }^\circ\text{C}$ or a sustained temperature of $\geq 38 \text{ }^\circ\text{C}$ ($100.4 \text{ }^\circ\text{F}$) for more than one hour refers to neutropenic fever and subjects should be referred for urgent evaluation and appropriate management.

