Magnesium ¹⁶ , Low (mEq/L; mmol/L)	1.2 to < 1.4 0.60 to < 0.70	0.9 to < 1.2 0.45 to < 0.60	0.6 to < 0.9 0.30 to < 0.45	< 0.6 < 0.30
Phosphate, Low (mg/dL; mmol/L) > 14 years of age	2.0 to < LLN 0.81 to < LLN	1.4 to < 2.0 0.65 to < 0.81	1.0 to < 1.4 0.32 to < 0.65	< 1.0 < 0.32
1 to 14 years of age	3.0 to < 3.5 0.97 to < 1.13	2.5 to < 3.0 0.81 to < 0.97	1.5 to < 2.5 0.48 to < 0.81	< 1.5 < 0.48
< 1 year of age	3.5 to < 4.5 1.13 to < 1.45	2.5 to < 3.5 0.81 to < 1.13	1.5 to < 2.5 0.48 to < 0.81	< 1.5 < 0.48
Potassium, High (mEq/L; mmol/L)	5.6 to < 6.0 5.6 to < 6.0	6.0 to < 6.5 6.0 to < 6.5	6.5 to < 7.0 6.5 to < 7.0	≥ 7.0 ≥ 7.0
Potassium, Low (mEq/L; mmol/L)	3.0 to < 3.4 3.0 to < 3.4	2.5 to < 3.0 2.5 to < 3.0	2.0 to < 2.5 2.0 to < 2.5	< 2.0 < 2.0
Sodium, High (mEq/L; mmol/L)	146 to < 150 146 to < 150	150 to < 154 150 to < 154	154 to < 160 154 to < 160	≥ 160 ≥ 160
Sodium, Low (mEq/L; mmol/L)	130 to < 135 130 to < 135	125 to < 130 125 to < 135	121 to < 125 121 to < 125	≤ 120 ≤ 120

PARAMETER	GRADE 1 MILD	GRADE 2 MODERATE	GRADE 3 SEVERE	GRADE 4 POTENTIALLY LIFE-THREATENING
Uric Acid, High (mg/dL; mmol/L)	7.5 to < 10.0 0.45 to < 0.59	10.0 to < 12.0 0.59 to < 0.71	12.0 to < 15.0 0.71 to < 0.89	≥ 15.0 ≥ 0.89
Hematology				
Absolute CD4+ Count, Low (cell/mm ³ ; cells/L) > 5 years of age (not HIV infected)	300 to < 400 300 to < 400	200 to < 300 200 to < 300	100 to < 200 100 to < 200	< 100 < 100
Absolute Lymphocyte Count, Low (cell/mm ³ ; cells/L) > 5 years of age (not HIV infected)	600 to < 650 0.600 x 10 ⁹ to < 0.650 x 10 ⁹	500 to < 600 0.500 x 10 ⁹ to < 0.600 x 10 ⁹	350 to < 500 0.350 x 10 ⁹ to < 0.500 x 10 ⁹	< 350 < 0.350 x 10 ⁹
Absolute Neutrophil Count (ANC), Low (cells/mm ³ ; cells/L) > 7 days of age	800 to 1,000 0.800 x 10 ⁹ to 1.000 x 10 ⁹	600 to 799 0.600 x 10 ⁹ to 0.799 x 10 ⁹	400 to 599 0.400 x 10 ⁹ to 0.599 x 10 ⁹	< 400 < 0.400 x 10 ⁹
2 to 7 days of age	1,250 to 1,500 1.250 x 10 ⁹ to 1.500 x 10 ⁹	1,000 to 1,249 1.000 x 10 ⁹ to 1.249 x 10 ⁹	750 to 999 0.750 x 10 ⁹ to 0.999 x 10 ⁹	< 750 < 0.750 x 10 ⁹
≤ 1 day of age	4,000 to 5,000 4.000 x 10 ⁹ to 5.000 x 10 ⁹	3,000 to 3,999 3.000 x 10 ⁹ to 3.999 x 10 ⁹	1,500 to 2,999 1.500 x 10 ⁹ to 2.999 x 10 ⁹	< 1,500 < 1.500 x 10 ⁹
Fibrinogen, Decreased (mg/dL; g/L)	100 to < 200 1.00 to < 2.00 OR 0.75 to < 1.00 x LLN	75 to < 100 0.75 to < 1.00 OR ≥ 0.50 to < 0.75 x LLN	50 to < 75 0.50 to < 0.75 OR 0.25 to < 0.50 x LLN	< 50 < 0.50 OR < 0.25 x LLN OR Associated with gross bleeding

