12.7. Appendix 7: Toxicity Management

ANEMIA

Grade 1 (mild) hemoglobin decrease:

Any hemoglobin decrease meeting the definition of Grade 1 must be repeated with the following additional tests:

1. peripheral blood smear
2. indirect bilirubin (abnormal if increased >50% from baseline)
3. haptoglobin (abnormal if ≤ 25 mg/dL)
4. reticulocyte count (abnormal if $\geq 4\%$)

If the additional tests are within the normal range, subjects may continue study medication. If one or more of the additional tests is abnormal or suggestive of hemolytic anemia as specified above, subjects will permanently discontinue study medication and be withdrawn from the trial. Subjects should be followed up until resolution of anemia.

Grade 2 (moderate) hemoglobin decrease:

Any hemoglobin decrease meeting the definition of Grade 2 must be repeated with the following additional tests:

5. peripheral blood smear
6. indirect bilirubin (abnormal if increased >50% from baseline)
7. haptoglobin (abnormal if ≤ 25 mg/dL)
8. reticulocyte count (abnormal if $\geq 4\%$)

If the additional tests are within the normal range, subjects may continue study medication. If one or more of the additional tests is abnormal or suggestive of hemolytic anemia as specified above, subjects will permanently discontinue study medication and be withdrawn from the trial. Consultation with a Hematologist should be considered. Subjects should be followed up until resolution of anemia.

Grade 3 (severe) or Grade 4 (potentially life threatening) hemoglobin decrease:

Any hemoglobin decrease meeting the definition of Grade 3 or 4 must be repeated with the following additional tests:

9. peripheral blood smear
10. indirect bilirubin
11. haptoglobin
12. reticulocyte count

Subjects will permanently discontinue study medication and be withdrawn from the trial. Consultation with a Hematologist should be considered. Subjects should be followed up until resolution of anemia.

TOTAL BILIRUBIN ELEVATION

Grade 1 (mild) bilirubin elevation (1.1 - 1.5 times ULN) or Grade 2 (moderate - 1.6-2.5 times ULN):

Any bilirubin value above the upper limit of normal must be repeated and fractionated (direct and indirect bilirubin). Subjects may continue study medication. Subjects should be followed up until resolution (return to baseline) of elevation.

Grade 3 (severe – 2.6-5.0 times ULN) or 4 (life-threatening - > 5.0 times ULN) bilirubin elevation:

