10.11.4. Safety Tables

Safety Tables					
No.	Population	IDSL / TST ID / Example Shell	Title	Programming Notes	Deliverable [Priority]
Adverse Events					
2.1.	Safety	LAI117010/ Table 2.1	Summary of Exposure Data	By subject and treatment	SAC
2.2.	Safety	LAI117010/ Table 2.2	Relationship of Adverse Event System Organ Classes, Preferred Terms, and Verbatim Text		SAC
2.3.	Safety	LAI117010/ Table 2.3	Summary of All Adverse Events by Treatment		SAC
2.4.	Safety	LAI117010/ Table 2.4	Summary of Drug-Related Adverse Events by Treatment		SAC
2.5.	Safety	LAI117010/ Table 2.5	Listing of Serious Adverse Events	By subject and treatment.	SAC
2.6.	Safety	LAI117010/ Table 2.6	Listing of Adverse Events Leading to Permanent Discontinuation of Study Drug or Withdrawal from Study	By subject and treatment	SAC
Labs					
2.7.	Safety	LAI117010/ Table 2.7	Listing of Reference Ranges for Clinical Laboratory Tests		SAC
2.8.	Safety	LAI117010/ Table 2.8	Summary of Clinical Haematology Laboratory Data by Treatment and Time		SAC
2.9.	Safety	LAI117010/ Table 2.9	Summary of Clinical Chemistry Laboratory Data by Treatment and Time		SAC
2.10.	Safety	LAI117010/ Table 2.10	Summary of Treatment Emergent Grade 2 or Higher Lab Abnormalities by Treatment	Summary of Treatment Emergent Lab toxicity only.	SAC
2.11.	Safety	LAI117010/ Table 2.11	Listing of Treatment Emergent Grade 2 or Higher Lab Abnormalities	By subject and treatment	SAC
2.12.	Safety	CP_LB5	Summary of All Urinalysis Data		SAC

Safety Tables					
No.	Population	IDSL / TST ID / Example Shell	Title	Programming Notes	Deliverable [Priority]
Vital Signs					
2.13.	Safety	LAI117010/ Table 2.13	Summary of Vital Signs by Treatment and Time	Include BP and HR only.	SAC
2.14.	Safety	LAI117010/ Table 2.14	Summary of Change from baseline in Vital Signs by Treatment and Time	Include BP and HR only.	SAC
2.15.	Safety	LAI117010/ Table 2.15	Listing of Vital Signs for Subjects with Abnormalities of Potential Clinical Importance	By subject and treatment	SAC
ECGs					
2.16.	Safety	LAI117010/ Table 2.16	Summary of ECG Findings		SAC
2.17.	Safety	LAI117010/ Table 2.17	Summary of ECG Values by Treatment and Time		SAC
2.18.	Safety	LAI117010/ Table 2.18	Summary of Change from Baseline in ECG Values by Treatment and Time		SAC
2.19.	Safety	LAI117010/ Table 2.19	Summary of Category of QTc Data by Treatment and Time		SAC
2.20.	Safety	LAI117010/ Table 2.20	Summary of Category of QTc Change from Baseline by Treatment and Time		SAC

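### The by-treatment lab toxicity table and its listing start at DAIDS Grade 2, so an ANC of 0.800 to 0.999 x10^9/L, which meets the neutropenia stopping rule but is Grade 1, is not shown in them.

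*SAP*

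**What the plan says.** SAP Appendix 8 sets out which values count as potentially clinically important. For laboratory data, section 10.8.1 uses DAIDS version 2.0 and says that "AE grade 2 and above of lab abnormalities will be listed by subject, period/treatment, visit, and actual date and time". Two displays in SAP 10.11.4 apply this cut-off: 2.10, a summary by treatment of treatment-emergent abnormalities, and 2.11, titled "Listing of Treatment Emergent Grade 2 or Higher Lab Abnormalities".

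Protocol 5.4.4 has a separate neutropenia rule. "Subjects with an absolute neutrophil count (ANC) less than" 1 x10^9/L are discontinued from study treatment.

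The haematology part of protocol Appendix 6 has a row headed "Absolute Neutrophil Count (ANC), Low". For participants more than 7 days old, Grade 1 is "800 to 1,000 0.800 x 10 ⁹ to 1.000 x 10 ⁹" and Grade 2 is "600 to 799 0.600 x 10 ⁹ to 0.799 x 10 ⁹" (cells/mm3, then cells/L).

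Protocol 4.6.2 describes neutropenia as common with rifabutin. It names haematology monitoring and the 5.4.4 rule as the mitigation. Safety of CAB alone and with RBT is a secondary objective (protocol section 3, SAP 2.2).

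**The concern.** The reporting threshold and the stopping threshold for the same parameter do not line up. Grade 2 starts below the value at which dosing must stop, so there is a band of ANC in which a subject is taken off treatment but contributes nothing to the table that summarises laboratory toxicity by treatment.

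At stake is how clearly the report describes one safety risk that the protocol singles out for rifabutin. Table 2.10 is where a reader would compare laboratory toxicity between CAB alone and CAB + RBT. It could have no neutrophil entry under CAB + RBT although a subject had met 5.4.4. The primary PK comparison is not affected.

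**Working it through.** The plan gives no figure to reproduce here. The check sets three thresholds side by side, using 1 x10^9/L = 1,000 cells/mm3.

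Inputs:
- Stopping rule: ANC <1,000 cells/mm3 (protocol 5.4.4).
- Grades: 1 = 800 to 1,000; 2 = 600 to 799; 3 = 400 to 599; 4 = below 400 cells/mm3 (protocol Appendix 6).
- Display filter: Grade 2 or higher (SAP 10.8.1, displays 2.10 and 2.11).

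| ANC, x10^9/L | Stopping rule met? | Grade | Shown in 2.10 and 2.11 if treatment-emergent? |
|---|---|---|---|
| 1.000 | no | 1 | no |
| 0.800 to 0.999 | **yes** | **1** | **no** |
| 0.600 to 0.799 | yes | 2 | yes |
| 0.400 to 0.599 | yes | 3 | yes |
| below 0.400 | yes | 4 | yes |

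The unshown stopping band is therefore 800 to 999 cells/mm3, and only that band. Entry requires ANC in the normal range (protocol 5.1, criterion 8), so a value in the band would normally be a fall from a normal screening result.

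The same comparison for other numeric limits:
- ALT: stopping at 3 x ULN or above (protocol Appendix 2). Grade 2 is 2.5 to <5.0 x ULN, so every stopping value is Grade 2 or higher. Liver events also have their own display, 2.25.
- Total bilirubin: discontinuation from Grade 3 (protocol Appendix 7), inside the filter.
- QTc: stopping above 500 msec or at a change above 60 msec (protocol 5.4.3). The SAP 10.8.2 limits are above 450 and above 60, so both are covered.

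The filter thus captures the ALT, bilirubin and QTc limits, but not all of the ANC limit.

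What the other displays would show for a subject at, say, 0.90:
- Listing 12: the value, its grade and a range flag, by subject, without a count.
- Table 2.8: haematology by treatment and time. Summaries include the minimum (protocol 9.4), so a scheduled 0.90 appears if it is the lowest in its cell. It does not give the number of subjects below 1.0, and unscheduled visits are left out of summary tables (SAP 10.5.3).
- SAP 10.7.1 and Listing 3: the subject's withdrawal with its reason, whether or not an AE was recorded. Table 1.2 summarises end-of-study records by treatment, but no reason category tied to 5.4.4 is specified.
- AE displays 2.3, 2.4 and 2.6: only if an AE is recorded, which for a laboratory value depends on the investigator judging it clinically significant (protocol 12.4.1).

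None of these is specified to count, by treatment, subjects who met the neutropenia stopping limit.

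**The case against.** The strongest reply is that displays 2.10 and 2.11 do exactly what their titles say. They are Grade 2 or higher toxicity displays, not stopping-rule displays, and neither document requires the reporting cut-off to match each stopping criterion. One DAIDS version is applied consistently. With about 15 subjects, anyone can read the complete graded haematology listing, and a withdrawal is listed with its reason in any case.

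Most of this stands, and it limits the point to one of presentation. What it leaves unanswered is that the limits for ALT, bilirubin and QTc are covered by their displays, while the one for the highlighted rifabutin risk is covered only in part, and no reason is given.

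Two stronger readings are tempting, and the documents do not support either.

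- A reader might infer that stopping-level neutropenia would be missing from the report, or that the report would show no neutrophil abnormality while subjects were being stopped for it. ANC below 0.80 is in both displays, and values from 0.800 to 0.999 are in Listing 12 with grade and flag. An empty neutrophil entry is possible in 2.10 and 2.11 alone.
- A reader might extend the point to haemoglobin, because Appendix 7 can lead to discontinuation at Grade 1. But a Grade 1 decrease is not itself a stopping event: "If one or more of the additional tests is abnormal or suggestive of hemolytic anemia as specified above, subjects will permanently discontinue study medication", and otherwise they may continue. Showing all Grade 1 haemoglobin values would not identify who met that condition.

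**Conclusion.** The point holds in a narrow form. ANC from 0.800 to 0.999 x10^9/L meets protocol 5.4.4 and is excluded from the by-treatment toxicity summary and its listing. This follows from the documents' own thresholds and needs no outside assumption.

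Its practical size cannot be estimated: the documents give no expected frequency for this band. For scale only, one subject among 15 is 1/15 = 6.7%. No data are lost, and no endpoint or estimate changes. It is a cheap improvement of minor severity to the reporting of a secondary safety objective.

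**What to change.** In SAP 10.8.1 and displays 2.10 and 2.11, add ANC <1.0 x10^9/L, labelled as meeting protocol 5.4.4, as a row by treatment in 2.10 and as entries in 2.11. State that unscheduled values count towards it. This needs an explicit exception, because protocol 9.4 and SAP 10.5.3 otherwise keep unscheduled results out of summary tables.

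The numeric criterion is preferable to showing ANC from Grade 1, since Grade 1 also includes exactly 1.000, which does not meet the rule. Keep Grade 2 or higher for all other parameters, haemoglobin included.

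The cost is a line of SAP text and one programming condition on laboratory data that are already to be graded in the analysis dataset. The downside is a few extra rows. The change concerns reporting only and implies nothing about the stopping rule itself.

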10.8.2. ECG

ECG Values of Potential Clinical Importance (Healthy Volunteers)

ECG Parameter	Potential Clinical Importance Range (PCI)	Unit
Absolute QTc Interval	>450	msec
Increase from baseline QTc	>60	msec
PR Interval	<110 and >220	msec
QRS Interval	<75 and >110	msec

10.8.3. Vital Signs

Vital Signs Values of Potential Clinical Importance (Healthy Volunteers)

Parameter	Potential Clinical Importance Range (PCI)	Unit
Systolic Blood Pressure	<85 and >160	mmHg
Diastolic Blood Pressure	<45 and >100	mmHg
Heart Rate	<40 and >110	bpm

10.9. Appendix 9: Model Specifications for Statistical Analysis

10.9.1. Statistical Analysis Assumptions and Model Specifications

Endpoint(s)	C _{max} , C _τ , AUC(0-τ), t _{1/2} and CL/F, if data permitted
Analysis	Linear Mixed Model

Specifications:
 
 For the Linear Mixed Model, model assumptions will be PK parameter following log-normal distribution. For drug-drug interaction assessment, an example of SAS code is included here. <pre>Proc Mixed; By parameter; class treatment subject; model logPKpar = treatment/ddfm=kr outpred=pred; random subject; lsmeans treatment; estimate 'B:A' treatment -1 1/cl alpha=0.1; /* (CAB+RTB) vs (CAB alone) */ run;</pre> 
 An example of SAS code to assess achievement of steady-state is included here. <pre>Proc Mixed; by dose; where day in (13,14); class subject; model logC0 = day/ddfm=kr cl alpha=0.1 solution; random intercept/subject=subject type=un solution; make 'solutionf' output=stat; run;</pre> 
repeat for Days 26,27,28 and Days 27,28
	

10.10. Appendix 10 - Abbreviations & Trade Marks

10.10.1. Abbreviations

Abbreviation	Description
ADaM	Analysis Data Model
ADaM IG	Analysis Data Model Implementation Guide
AE	Adverse Event
ANOVA	Analysis of Variance
AUC	Area under concentration-time curve
AUC(0- τ)	Area under the concentration-time curve over one dosing interval
BESM	Bioanalytical External Study Monitors
BIB	Bioanalysis, Immunogenicity and Biomarkers
CDISC	Clinical Data Interchange Standards Consortium
CI	Confidence Interval
CL/F	The apparent oral clearance
C _{max}	Maximum observed concentration
CP	Clinical Programming
CPMS	Clinical Pharmacology Modelling & Simulation
CPSSO	Clinical Pharmacology Sciences and Study Operations
CRF	Case record form
CS	Clinical Statistics
C _t	Concentration at the end of the dosing interval
CV	Coefficient of Variation
CVb/CVw	Coefficient of Variation (Between)/Coefficient of Variation (Within)
DAIDS	Division of Acquired Immune Deficiency Syndrome
DBF	Database Freeze
DBR	Database Release
GSK	GlaxoSmithKline
HARP	Harmonized Analysis and Reporting Process
IDSL	Integrated Data Standards Library
LLQ	Lower limit of quantification
NC	Not Calculable
NQ	Non-quantifiable concentration measured as below LLQ
PK	Pharmacokinetic
QSci	Quantitative Sciences
RAP	Reporting and Analysis Plan
RBT	Rifabutin
RTF	Rich Text Format
SAS	Statistical Analysis System
SD	Standard deviation
SDTM	Study Data Tabulation Model
SRP	Statistics Resourcing and Programming
t _{1/2}	Terminal phase half-life
T _{max}	Time of occurrence of C _{max}

10.10.2. Trademarks

Trademarks of ViiV Healthcare
NONE

Trademarks not owned by ViiV Healthcare
Mycobutin
SAS
WinNonlin

10.11. Appendix 11: List of Data Displays

10.11.1. Data Display Numbering

The following numbering will be applied for RAP generated displays:

Section	Tables	Figures
Study Population	1.1 to 1.n	N/A
Safety	2.1 to 2.n	N/A
Pharmacokinetic	3.1 to 3.n	3.1 to 3.n
Section	Listings	
ICH Listings	1 to x	
Other Listings	x+1 to y	

10.11.2. Mock Example Referencing

All displays will be provided with an example from previous CAB studies LAI117010 and LAI117011 or mock examples are provided.

10.11.3. Study Population Tables

Study Population Tables					
No.	Population	IDSL / TST ID / Example Shell	Title	Programming Notes	Deliverable [Priority]
Subject Disposition					
1.1.	Safety	LAI117010/ Table 1.1	Summary of Analysis Populations	by Overall	SAC
1.2.	Safety	LAI117010/ Table 1.2	Summary of End of Study Record by Treatment and Overall	By subject and treatment	SAC
1.3.	Safety	LAI117010/ Table 1.3	Listing of End of Study Record	By subject	SAC
Demographics and Enrolment Information					
1.4.	Safety	LAI117010/ Table 1.5	Summary of Demographic characteristics	Include BMI, Race detail	SAC
1.5.	Safety	LAI117010/ Table 1.6	Summary of Race for Safety Population	By treatment and Overall	SAC
1.6.	Safety	LAI117010/ Table 1.7	Listing of Concomitant Medication	By Subject. Change from listing to summary if more than 3 pages	SAC
1.7.	Safety	LAI117010/ Table 1.8	Listing of Genetics Subject Accountability		SAC
1.8.	Safety	LAI117010/ Table 1.9	Listing of Treatment Non-Compliance		SAC
1.9.	Safety	LAI117010/ Table 1.10	Listing of Subjects with Protocol Deviations		SAC
1.10.	Safety	LAI117010/ Table 1.11	Summary of Screening Information		SAC
1.11.	Safety	LAI117011/ Table 1.11	Age Group Breakdown for the Trial	For Eudra posting	

10.11.4. Safety Tables

Safety Tables					
No.	Population	IDSL / TST ID / Example Shell	Title	Programming Notes	Deliverable [Priority]
Adverse Events					
2.1.	Safety	LAI117010/ Table 2.1	Summary of Exposure Data	By subject and treatment	SAC
2.2.	Safety	LAI117010/ Table 2.2	Relationship of Adverse Event System Organ Classes, Preferred Terms, and Verbatim Text		SAC
2.3.	Safety	LAI117010/ Table 2.3	Summary of All Adverse Events by Treatment		SAC
2.4.	Safety	LAI117010/ Table 2.4	Summary of Drug-Related Adverse Events by Treatment		SAC
2.5.	Safety	LAI117010/ Table 2.5	Listing of Serious Adverse Events	By subject and treatment.	SAC
2.6.	Safety	LAI117010/ Table 2.6	Listing of Adverse Events Leading to Permanent Discontinuation of Study Drug or Withdrawal from Study	By subject and treatment	SAC
Labs					
2.7.	Safety	LAI117010/ Table 2.7	Listing of Reference Ranges for Clinical Laboratory Tests		SAC
2.8.	Safety	LAI117010/ Table 2.8	Summary of Clinical Haematology Laboratory Data by Treatment and Time		SAC
2.9.	Safety	LAI117010/ Table 2.9	Summary of Clinical Chemistry Laboratory Data by Treatment and Time		SAC
2.10.	Safety	LAI117010/ Table 2.10	Summary of Treatment Emergent Grade 2 or Higher Lab Abnormalities by Treatment	Summary of Treatment Emergent Lab toxicity only.	SAC
2.11.	Safety	LAI117010/ Table 2.11	Listing of Treatment Emergent Grade 2 or Higher Lab Abnormalities	By subject and treatment	SAC
2.12.	Safety	CP_LB5	Summary of All Urinalysis Data		SAC

Safety Tables					
No.	Population	IDSL / TST ID / Example Shell	Title	Programming Notes	Deliverable [Priority]
Vital Signs					
2.13.	Safety	LAI117010/ Table 2.13	Summary of Vital Signs by Treatment and Time	Include BP and HR only.	SAC
2.14.	Safety	LAI117010/ Table 2.14	Summary of Change from baseline in Vital Signs by Treatment and Time	Include BP and HR only.	SAC
2.15.	Safety	LAI117010/ Table 2.15	Listing of Vital Signs for Subjects with Abnormalities of Potential Clinical Importance	By subject and treatment	SAC
ECGs					
2.16.	Safety	LAI117010/ Table 2.16	Summary of ECG Findings		SAC
2.17.	Safety	LAI117010/ Table 2.17	Summary of ECG Values by Treatment and Time		SAC
2.18.	Safety	LAI117010/ Table 2.18	Summary of Change from Baseline in ECG Values by Treatment and Time		SAC
2.19.	Safety	LAI117010/ Table 2.19	Summary of Category of QTc Data by Treatment and Time		SAC
2.20.	Safety	LAI117010/ Table 2.20	Summary of Category of QTc Change from Baseline by Treatment and Time		SAC
2.21.	Safety	LAI117010/ Table 2.21	Listing of ECG Values for Subjects with Abnormalities of Potential Clinical Importance	By subject and treatment	SAC
2.22.	Safety	LAI117010/ Table 2.22	Listing of Clinically Significant ECG Abnormalities	List all data for a subject with clinically significant abnormalities	SAC
2.23.	Safety	LAI117011/ Table 2.17	Summary of Serious Adverse Events by Preferred Term Including Drug-related Status and Fatal Status	Eudra posting table	SAC
2.24.	Safety	LAI117011/ Table 2.18	Summary of Non-Serious Adverse Events by Preferred Term with Occurrences >5%	Eudra posting table	SAC

Safety Tables					
No.	Population	IDSL / TST ID / Example Shell	Title	Programming Notes	Deliverable [Priority]
2.25.	Safety	IDSL LIVER5	Listing of Liver Monitoring and stopping Event Reporting	IDSL standard for liver event	SAC

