4.6.2. Risk Assessment-Rifabutin

Adverse reactions identified through post-marketing surveillance by system organ class (SOC) include: blood cell disorders (agranulocytosis, lymphopenia, granulocytopenia, neutropenia, leukopenia, and thrombocytopenia), immune system disorders (hypersensitivity, bronchospasm, rash, and eosinophilia), and gastrointestinal disorders (*Clostridium difficile* colitis/ *Clostridium difficile* associated diarrhea). Pyrexia, rash and other hypersensitivity reactions such as eosinophilia and bronchospasm might occur, as has been seen with other anti-bacterials. A limited number of skin discolorations have been reported. Hypersensitivity to rifamycins has been reported including flu-like symptoms, bronchospasm, hypotension, urticaria, angioedema, conjunctivitis, thrombocytopenia or neutropenia. See below for the Rifabutin risk assessment and mitigation strategy for this protocol.

Neutropenia: Neutropenia is commonly experienced in patients receiving RBT and rapidly resolves with discontinuation of RBT. Subjects will have frequent hematology laboratory monitoring and the neutropenia stopping rule is in place, see Section 5.4.4.

Uveitis: Subjects will be followed for development of ocular AEs since RBT has been associated with this complication, although it is rare when administered as 300 mg/day. Uveitis can develop from 2 weeks to more than 7 months after initiation of RBT treatment [Tseng, 1995]. Discontinuation of RBT or dose reduction generally results in resolution of uveitis and complete recovery of visual acuity is typical with drug withdrawal and topical treatment. Subjects with evidence of new ocular symptoms consistent with uveitis (eye pain, eye redness, light sensitivity, blurriness or change in vision, that is not attributed to allergic, infectious (bilateral viral/bacterial conjunctivitis or HSV keratitis), acute angle-closure glaucoma, corneal abrasions, scleritis, or secondary to trauma including intraocular foreign body will be discontinued from study treatment, and referred to ophthalmology for evaluation and appropriate treatment. Refer to Ocular stopping criteria, Section 5.4.1

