7.3.4. Vital Signs

- Vital signs will be measured in semi-supine position after 10 minutes rest and will include systolic and diastolic blood pressure and pulse rate. Temperature will also be obtained as part of the Vital Signs assessment.
- Measurements that deviate substantially from previous readings will be repeated immediately.
- Two (2) blood pressure (BP) and heart rate (HR) measurement will be taken at pre-dose on Day 1, at least 1 minute apart. The mean value recorded at pre-dose will be classified as baseline. Single BP and HR will be obtained at all other time points during the study. A single Temperature (TT) assessment will be obtained at Pre-dose as well as other time points during the study as specified in the Time and Event Table Section [7.1](#).

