2. SUMMARY OF KEY PROTOCOL INFORMATION

2.1. Changes to the Protocol Defined Statistical Analysis Plan

There were no changes or deviations to the originally planned statistical analysis specified in the protocol amendment 2 (Dated: 29-Jun-2017).

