2.2. Study Objective(s) and Endpoint(s)

Objectives	Endpoints
Primary Objectives	Primary Endpoints

 To compare steady state CAB exposure following 30 mg oral dose once daily with and without RBT 300 mg once daily. 	
 Plasma CAB AUC(0-τ), C_{max}
Secondary Objectives	Secondary Endpoints

 To describe the pharmacokinetic (PK) of CAB 30 mg oral dose once daily administered alone and co-administered with RBT. 	
 Plasma CAB C_t, t_{max}, t_{1/2} and CL/F

 To assess the safety and tolerability of CAB 30 mg oral dose administered alone and in combination with RBT 300 mg once daily. 	
 Safety and tolerability parameters, including adverse events, concurrent medication, clinical laboratory screens, electrocardiogram (ECG), and vital signs assessments.

AUC_(0-t) = area under the plasma concentration time curve from time zero to the last quantifiable time point C_{max} = maximum observed concentration C_t = last quantifiable concentration t_{max} = time of maximum observed concentration t_{1/2} = the elimination half-life CL/F = apparent oral clearance
	

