10.2. Appendix 2: Data Management

10.2.1. Data Format and Process

Data Type	Source	Format of Data	Planned Date of Final File	Responsibility
Safety	PIMS>SI data	SI>STDM	DBF	Accenture
PK Concentration	SMS2000 data file	dat file	DBF	BIB/BESM
PK Concentration (ADPC), WNL File	PK concentration data (SDTM PC), exposure (EX) and demography (DM) datasets ²	ADaM, CSV file	DBF + 5 Days ¹	QSci
PK Parameters	WNL file	CSV file	PK Concentration, WNL file + 10 Days	CPMS

1. Provided SDTM PC, EX and DM are in time and clean
2. PK concentration data is released via SMS2000 by Bioanalysis, Immunogenicity and Biomarkers (BIB)/Bioanalytical External Study Monitors (BESM) and the SDTM PC contains date/times and PK sample ID

CONFIDENTIAL

205712

Procedure	Screen ¹	Day -1	Treatment Period 1 Day													Treatment Period 2 Day													Early Withdrawal / Follow-up ~10-14 days		
			1	2	3	4	5	6	7	8	9	10	11	12	13	14	15	16	17	18	19	20	21 ²	22	23	24	25	26 ²		27	28
Safety Laboratory assessments	X	X												X														X			X
12-lead ECG ⁶	X		X												X														X		X
Vital signs (Including Temperature) ⁶	X		X												X							X							X		X
Administer CAB 30 mg once daily ⁷			X	X	X	X	X	X	X	X	X	X	X	X	X	X	X	X	X	X	X	X	X	X	X	X	X	X	X		
Administer RBT 300 mg once daily ⁷																X	X	X	X	X	X	X	X	X	X	X	X	X			
Dispense CAB ⁸			X																												
Dispense CAB ⁹ and RBT ¹⁰																X															
Pharmacokinetic Sampling ¹¹														X	X	X											X	X	X	X	
Admit to Unit		X												X														X			
Discharge from Unit			X													X													X		
Outpatient Visit	X																					X					X			X	

Procedure	Screen ¹	Day -1	Treatment Period 1 Day													Treatment Period 2 Day							Early Withdrawal / Follow-up ~10-14 days									
			1	2	3	4	5	6	7	8	9	10	11	12	13	14	15	16	17	18	19	20		21 ²	22	23	24	25	26 ²	27	28	29
Drug accountability													X									X				X	X					
Genetic sample ¹²			←-----→																													
SAE Review	←-----→																															
AE Review	←-----→																															
Concomitant medication review	←-----→																															

CONFIDENTIAL

205712

1. Screening must be performed within 30 days prior to receiving the dose of CAB on Day 1.
2. Day 21 and Day 26 is an outpatient visit.
3. An ocular assessment will be performed only for subjects who experience eye symptoms.
4. A brief symptom directed physical exam will be completed as needed.

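### Temperature is collected as a vital sign, but the SAP's vital-sign tables and limits cover only blood pressure and heart rate, so an isolated raised temperature reaches the Appendix 11 outputs only if recorded as an adverse event

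*SAP*

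**What the plan says.** The secondary safety endpoint in SAP 2.2 covers "clinical laboratory screens, electrocardiogram (ECG), and vital signs assessments" without excluding any component. Protocol 7.3.4 states: "Temperature will also be obtained as part of the Vital Signs assessment". The SAP's own time and events schedule labels the row "Vital signs (Including Temperature", so both documents treat temperature as a vital sign.

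The reporting sections are narrower. The programming note for Table 2.13 (values) and Table 2.14 (change from baseline) is "Include BP and HR only". SAP 10.8.3 has three rows of PCI limits: systolic pressure, diastolic pressure and heart rate. DAIDS toxicity grades are applied to laboratory results (10.8.1), not to vital signs.

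SAP Table 6 has two vital-sign rows. One is for vital-sign values, with summaries and an individual listing whose footnote promises a toxicity grade or a high/low flag. The other is for measurements outside the PCI range. In Appendix 11 every vital-sign listing depends on a PCI limit being breached.

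**The concern.** A collected component of a stated endpoint is dropped by an explicit programming instruction, and no reason is given.

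Temperature has particular relevance here. Protocol 4.6.2 warns that "Pyrexia, rash and other hypersensitivity reactions such as eosinophilia and bronchospasm might occur" and counts vital signs among the assessments that may help detect hypersensitivity early. Low neutrophils together with fever is the state that Protocol 5.4.4 says "refers to neutropenic fever and subjects should be referred for urgent evaluation and appropriate management". Appendix 7 uses temperature as one sign in its Grade 1 and Grade 2 rash and allergic-reaction guidance.

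Rifabutin is given only in Period 2, so a by-treatment temperature summary would be the direct descriptive comparison of CAB alone with RBT + CAB. The plan provides that comparison for BP and HR but not for temperature.

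**Working it through.** The plan states no figure to reproduce. The check traces one hypothetical subject through every vital-sign display in Appendix 11.

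**Subject:** raised temperature at a scheduled visit, with all BP and HR values inside the 10.8.3 limits (systolic 85 to 160 mmHg, diastolic 45 to 100 mmHg, heart rate 40 to 110 bpm).

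| Display | What it admits | Is the temperature shown? |
|---|---|---|
| Table 2.13 | BP and HR values | No, excluded by the note |
| Table 2.14 | BP and HR change from baseline | No, excluded by the note |
| Table 2.15 | Subjects with a PCI abnormality | No, subject not selected |
| Listing 17 | Values outside a PCI limit | No, temperature has no limit |
| Listing 18 | All vital signs of subjects with any PCI value | No, subject not selected |

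Result: 0 of 5 displays. The condition on BP and HR matters, because a febrile subject with a heart rate above 110 bpm would enter Listing 18, where the temperature could be shown.

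**Number of readings.** The vital-signs row of the SAP schedule marks screening and Days 1, 14, 21 and 28, plus follow-up. One Period 1 column is damaged in the copy used, so the days were aligned on the PK-sampling and dispensing rows and should be confirmed on a clean page.

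- All readings: 6 visits × 15 subjects = 90.
- Post-baseline readings: 4 × 15 = 60. These are 15 on CAB alone (Day 14), 30 on RBT + CAB (Days 21 and 28) and 15 at follow-up.
- If only the 12 planned completers contribute: 6 × 12 = 72 in all and 4 × 12 = 48 post-baseline, plus whatever the withdrawn subjects supplied.

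These are counts of unsummarised readings, not an expected number of missed fevers. The documents give no fever rate from which to estimate that.

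**Baseline.** Table 7 names BP and pulse rate in its vital-signs row, but the sentence above it makes the latest pre-dose assessment the baseline for any endpoint not noted in the table. Protocol 9.4 has a similar default, and 7.3.4 schedules a single pre-dose temperature. Change from baseline can therefore be computed without a new definition.

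**Table 6 against Appendix 11.** For laboratory data, Appendix 11 turns the Table 6 marks into full listings: the notes for Listings 11 and 12 call for every test. For vital signs, only the PCI-dependent Listings 17 and 18 appear. Either the listing of values was meant to be full and is missing, or Listing 18 was meant to satisfy it. ECG has the same two marks and only PCI-dependent value listings (14 and 15), so the second reading is possible. The documents do not settle it.

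**The case against.** The strongest reply is that a fever that matters would be reported elsewhere. Abnormal vital signs that the investigator judges clinically significant are adverse events (Protocol Appendix 4). They then reach Table 2.3, Listing 10, Table 2.4 if judged related, and Table 2.6 if they lead to discontinuation. This stands. A reader might infer that fevers would be invisible in the whole report; the documents do not support that. What remains is a measured temperature not recorded as an adverse event, and any shift in temperature between treatments. BP and HR can also generate adverse events, yet they are summarised.

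SAP 2.1 says "There were no changes or deviations to the originally planned statistical analysis specified in the protocol amendment 2", and a reader might infer that the omission breaks that statement. It does not: Protocol 9.4 and 9.4.2 promise descriptive safety summaries to sponsor standards, leave the detail to the analysis plan, and name no temperature table.

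Nor does the omission disable a safety rule. Investigators apply Protocol 5.4.4 and Appendix 7 in real time, and no SAP display feeds them. In 5.4.4 discontinuation depends on the neutrophil count alone; in Appendix 7 the temperature sign applies to subjects who already have a rash or an allergic reaction.

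Finally, Table 6 may intend a full listing that would show every temperature. That is fair, but Appendix 11 is the list that programmers work from, and it contains none.

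**Conclusion.** The point holds as a gap in descriptive safety reporting. By explicit instruction, a measured vital sign linked to a named rifabutin risk is left out of the two summaries, and the PCI-dependent displays cannot pick it up on its own. Up to 60 post-baseline readings are affected, at least 48 with 12 completers.

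It is a modest point. The primary PK comparison is untouched, no hypothesis is tested, and fevers judged clinically significant are still reported as adverse events. It would also go too far to say that temperature lacks a baseline, since the default in 10.5.2.1 covers it.

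The conclusion assumes that Appendix 11 is the complete list of displays. The mock shells in SAP Appendix 12 and the earlier-study shells it relies on could not be checked; a shell that included temperature would contradict the programming note for Tables 2.13 and 2.14.

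**What to change.** 1. Reword the programming note for Tables 2.13 and 2.14 so that it names BP, HR and temperature. The default baseline already applies; naming temperature in Table 7 is optional.
2. Align Appendix 11 with Table 6 by adding a listing of all vital signs, including every temperature, by subject, treatment and visit.
3. If the listing carries a flag, take it from the existing Fever row in Protocol Appendix 6 and label it as a display aid only. That row is restricted to non-axillary readings, Protocol 7.3.4 gives no route of measurement, and the protocol uses 38.0, 38.3 and 38.5 °C in different places for different purposes. The footnote should therefore state the source of the flag and the route.

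If the sponsor prefers to leave temperature out, the SAP should say so and give the reason.

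The cost is a wording change, one more parameter in two existing tables and one more listing. No new data, clinical threshold or management rule is involved.
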